#### Non-hematologic

- a. Any grade  $\geq$  4 event.
- b. Any grade  $\geq$  3 non-hematologic toxicity with the following exceptions:
  - i. Grade 3 fatigue, asthenia, anorexia, fever, or constipation.
  - ii. Grade 3 nausea, vomiting or diarrhea not requiring tube feeds, TPN or hospitalization.
  - iii. Grade 3 or 4 non-clinically significant and transitory laboratory abnormalities that resolve to ≤ grade 1 or baseline within 7 days, except for any possible Hy's Law event (Refer to 8.3.2)
  - iv. Alopecia
  - v. Tumor lysis syndrome not requiring dialysis
  - vi. DVT responsive to anticoagulation

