### 4.2.4 Definition of Dose Limiting Toxicities

DLTs will be assessed for each patient within the DLT window. The DLT window is defined as the time from Cycle 1 Day 1 to Cycle 1 Day 21. Common terminology criteria for adverse events (CTCAE) v5.0 will be used to grade all adverse events (AE) and to provide management guidelines for administrational toxicity. Any of the following AEs which cannot be incontrovertibly attributed to CLL or CLL disease progression will be defined as a DLT.

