#### General

- a. Treatment delays > 21 days.
- b. Any grade 5 event.

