# 6 STUDY INTERVENTION

### 6.1 Administration Schedule

Treatment will be administered on an outpatient basis. No investigational or commercial agents or therapies other than those described below may be administered with the intent to treat the patient's CLL.

Regimen Description					
Agent	Precautions	Dose	Route	Schedule	Cycle Length
RP-3500	Take with 8 oz of water at approximately the same times each day (±2 hours)	Capsule*	Oral	Once daily; intermittent weekly dosing of 2 days on and 5 days off	21 days (3
Olaparib	Take with 8 oz of water at approximately the same times each day (±2 hours)	Capsule*	Oral	Twice daily; intermittent weekly dosing of 2 days on 5 days off	weeks)
* Doses as appropriate for assigned dose level					

Study medications should be taken at approximately the same time every day. Study medication should not be crushed, chewed, or altered in any way. Subjects should not take extra medication for any reason nor should they re-administer in the case of vomiting after

administration. If a dose is missed outside of the dosing window, the dose should not be made up but rather dosing should continue at their regularly scheduled time.

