# 7.6.3 Pharmacokinetic Studies

Plasma samples will be collected at defined time points in section 1.5.1 to assess the pharmacokinetics of RP-3500 and olaparib.

7.6.3.1 On C1D1 and C1D15, blood samples will be collected at pre-dose and 0.5, 1, 2, 4, and 24 hours post dose. Patients will take their doses of RP-3500 and olaparib in the infusion room or clinic after the pre-dose PK blood draw has occurred and at the instruction of the research team. For the 24 hour post dose collection, patients will have PK study blood drawn prior to taking their C1D2 and C1D16 drug doses.

7.6.3.2 On C1D8, blood samples will be collected at pre-dose, 0.5, 1, 2, and 4 hours post dose. Patients will take their doses of RP-3500 and olaparib in the infusion room or clinic after the pre-dose PK blood draw has occurred and at the instruction of the research team.

Blood samples will be processed to plasma and RP-3500 and olaparib will be analyzed by validated LC/MS-MS bioanalytical methods. PK parameters for RP-3500 and olaparib will be calculated using non-compartmental analysis: area under the concentration-time curve (AUC) from time 0 to last quantifiable concentration (AUC0-last); AUC from time 0 to infinity (AUC0-inf); maximum observed plasma concentration ( $C_{max}$ ); time to reach Cmax ( $T_{max}$ ) and terminal elimination half-life ( $t_{1/2}$ ). The effect of olaparib on the AUC0-last and AUC0-inf and Cmax of RP-3500 will be compared to respective monotherapy doses from other studies performed with RP-3500. RP-3500 and olaparib may also be analyzed using population PK methods.

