#### 8.3.2 Hy's Law Cases

It is important to identify possible cases of Drug-Induced Liver Injury (DILI) early. Total bilirubin, AST, and ALT should be regularly monitored for elevations indicative of liver damage. Subjects who experience a transaminase elevation above three times the ULN should be monitored frequently to determine if the elevation is transient. Transient elevations are an indication of adaption and these subjects may be identified as "adaptors." However, should a transaminase elevation be followed by total bilirubin (TBili) increase, a DILI could be occurring. Any laboratory abnormalities meeting the following criteria should be reported within 24 hours of awareness:

• AST or ALT elevation > 3 x ULN; and

- Total bilirubin > 2 x ULN; and
- Absence of cholestasis; and
- No alternative explanation for the elevations (e.g., impaired glucuronidation capacity caused by genetic [Gilbert syndrome]; viral hepatitis A, B, or C, preexisting or acute liver disease; or another drug capable of causing the observed injury).

Investigators should conduct reasonable investigations to rule out other possible etiologies. Investigators should take into consideration the subject's use of ethanol, acetaminophen, recreational drugs, herbal supplements, and medical history. A potential Hy's Law case will not be considered a confirmed case until all results and considerations have excluded alternative etiologies.

Possible cases of DILI will be promptly reported to the FDA and Repare Therapeutics prior to full work up to rule out other etiologies. Reporting should be completed on a MedWatch 3500A form and should include all available information, including the likelihood that the drug caused the event. Subjects should be closely followed until the resolution of the event.

Subjects who experience possible DILI should be managed per the Dose Modification Guidelines.

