# 9.2.1 DLT Evaluable Population

For dose-finding, subjects who receive at least one dose of any study drug during the DLT evaluation period will be considered evaluable for a DLT event. Only subjects who have experienced a DLT event or received 80% of the expected doses during the DLT period will be included when evaluating dose level changes.

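### A possible Hy's Law event with AST/ALT and bilirubin both below grade 3 is not a DLT under section 4.2.4 when graded by its laboratory values, and no dose-modification row requires a hold

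*Combined protocol and SAP*

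**What the plan says.** Section 4.2.4, under Non-hematologic, makes any event of grade 4 or higher a DLT (item a), and any of grade 3 or higher subject to listed exceptions (item b). Exception b.iii exempts non-clinically significant, transitory grade 3 or 4 "laboratory abnormalities that resolve to ≤ grade 1 or baseline within 7 days, except for any possible" Hy's Law event, with a reference to 8.3.2. Hy's Law appears nowhere else in the DLT definition. Under General, the section also lists grade 5 events and "Treatment delays > 21 days". On timing it says "The DLT window is defined as the time from Cycle 1 Day 1 to Cycle 1 Day 21".

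Section 8.3.2 joins four criteria: AST or ALT above 3 x ULN, total bilirubin above 2 x ULN, absence of cholestasis, and "No alternative explanation for the elevations". No grade is attached. Events must be reported within 24 hours, and possible DILI goes to the FDA and the manufacturer before the work-up is complete. On management it says "Subjects who experience possible DILI should be managed per the Dose Modification Guidelines".

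Those guidelines are in 6.6. Table 14 has rows for nausea, vomiting, diarrhea, fatigue, dyspnea and other non-hematologic toxicity. The last of these starts at grade 3, and there is no liver row.

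On who counts for the dose decision, 9.2.1 says "Only subjects who have experienced a DLT event or received 80% of the expected doses during the DLT period will be included".

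**The concern.** An exception to an exemption only returns an event to the parent rule, and the parent rule here needs grade 3. The carve-out in b.iii therefore restores transient grade 3 or 4 Hy's Law events as DLTs. It cannot turn a lower-grade event into one. Where the authors wanted a DLT regardless of grade they wrote one: febrile neutropenia counts at any grade. Hy's Law has no such line.

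At stake is the escalation count. DLTs drive Table 8 and the isotonic estimate that selects the MTD (4.2.3). A recognised signal of serious liver injury that is not called a DLT enters neither. The pointer in 8.3.2 leads to no row that stops drug for such an event, and this second gap applies in phase II as well.

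**Working it through.** **1. Where the gap lies.** Let grade 3 start above A x ULN for AST/ALT and above B x ULN for bilirubin. The documents adopt CTCAE v5.0 but print no cut points, so A and B are assumptions, and baseline is taken as normal. The uncaptured region is AST/ALT above 3 and up to A, together with bilirubin above 2 and up to B.

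- A = 5, B = 3: AST/ALT 3–5 x ULN with bilirubin 2–3 x ULN.
- A = 4, B = 2.5: AST/ALT 3–4 x ULN with bilirubin 2–2.5 x ULN.
- A ≤ 3 or B ≤ 2: no gap.

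If either value reaches grade 3, item b applies, the b.iii carve-out works, and Table 14's last row requires a hold.

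**2. Table 8 reproduced.** With a uniform prior, the posterior for k DLTs in n patients is Beta(1+k, 1+n−k). Keys have width 0.33 − 0.25 = 0.08, and the strongest key decides. U applies if P(p > 0.30 | data) > 0.95 with n ≥ 3. The prior and the 0.95 cut-off are assumptions. All 75 printed cells for n = 1 to 12 match. For example, 3/3 gives 1 − 0.3^4 = 0.992, so U. For 2/3 the result is 1 − (4 × 0.3^3 × 0.7 + 0.3^4) = 0.916, so not U.

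**3. Dosing days in the window.** The schedule is "intermittent weekly dosing of 2 days on and 5 days off". Section 7.6.3 confirms the second days of weeks 1 and 3: "patients will have PK study blood drawn prior to taking their C1D2 and C1D16 drug doses". Dosing days are therefore 1–2, 8–9 and 15–16, six in all. Reading expected doses as these six days:

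- one day missed: 5/6 = 83%, evaluable;
- one week held (Days 8–9 or 15–16): 4/6 = 67%, below 80%, not evaluable unless a DLT is called;
- event after Day 16: 6/6 = 100%, evaluable.

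**4. Effect of one uncounted event on Table 8.** At the default cohort totals, these are the counts at which the decision changes in at least one case (E escalate, S stay, D de-escalate, U unacceptable):

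| Event counted | Not counted, patient kept | Not counted, patient dropped |
|---|---|---|
| 1/3 D | 0/3 E | 0/2 E |
| 3/3 U | 2/3 D | 2/2 D |
| 2/6 D | 1/6 E | 1/5 E |
| 4/6 U | 3/6 D | 3/5 D |
| 3/9 D | 2/9 E | 2/8 S |
| 5/9 U | 4/9 D | 4/8 D |
| 3/12 S | 2/12 E | 2/11 E |
| 4/12 D | 3/12 S | 3/11 S |
| 7/12 U | 6/12 D | 6/11 U (no change) |

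Over all n from 1 to 12 there are 1 + 2 + … + 12 = 78 pairs with at least one DLT. Comparing (k, n) with (k−1, n) changes 28 of them. Comparing (k, n) with (k−1, n−1) changes 21. Every change is to a less cautious decision.

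**The case against.** Several points weigh on the other side.

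- **Grading the diagnosis.** 8.3.2 describes a clinical judgement, not just two values. Under 8.2.1 an event that CTCAE does not list is graded by Table 18, where a severe event needing intervention is grade 3. A possible DILI graded that way would be a DLT. This stands as a route, but nothing requires it, and whether CTCAE lists such a term cannot be settled from the documents.
- **The delay item.** A reader might infer that a delay of more than 21 days can never be a DLT, because it cannot be completed by Day 21. The documents do not support that firmly: it would make a listed item inoperative, and a delay that starts in the window could be read as counting. That reading is not stated either.
- **Holding drug.** A reader might also infer that the protocol prevents a hold. It does not. Section 6.4 permits interruptions, 6.5 recommends consulting the PI and medical monitor, 6.6 allows modification, and 6.9.1 lets the investigator stop treatment. All of these are discretionary. The instruction in 6.6.5 to hold both drugs when the cause is unclear follows a sentence about AEs that have guidelines for both drugs, and no such liver guideline exists below grade 3.
- **The 80% rule.** It affects any non-DLT hold, not only this event. The one-dose eligibility statement in 4.2.4 does not override it, since 9.2.1 limits dose-level decisions expressly.
- **Safeguards.** DSMC and PI cohort review (4.2.2), 24-hour reporting (8.3.2) and Medical Monitor approval of escalations (8.4) all reduce the risk. None makes the event count as a DLT.

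**Conclusion.** The gap is real but narrow. It covers an event meeting 8.3.2 with both values below grade 3, graded by those values, and it exists only if A is above 3 and B above 2. The intent was probably that every possible Hy's Law event counts, but the text does not say so. Raised baselines are not covered by the ranges above.

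The consequence is one missing DLT, which at the most common early counts moves the decision from de-escalate to escalate. The exclusion under 9.2.1 is a further consequence only if at least two of six dosing days are missed and no DLT is called.

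The 28 of 78 and 21 of 78 counts should not be read as a risk. They weight every cell equally, include sizes outside cohorts of three, and in one case compare 1/1 with 0/0. Any uncounted DLT would give the same table. The documents give no event frequency. This should be corrected, with medium confidence in its practical weight.

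**What to change.** Add a stand-alone line to 4.2.4: *any event meeting the 8.3.2 criteria, regardless of grade, counted as a DLT unless the work-up establishes an alternative cause before the cohort dose decision*. The last clause is needed because 8.3.2 has possible cases reported before other causes are excluded. Once the event is a DLT, the patient stays in the 9.2.1 count whatever share of doses was taken.

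Add a hepatic/possible DILI row to Table 14 that holds both drugs pending work-up. Its rechallenge terms, set by the clinical team, should apply outside the DLT window, in phase II, or when an alternative cause is established, because 6.5 removes a patient with a DLT in escalation from protocol.

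The cost is one line and one row. Slightly more events would count as DLTs and lead to removal. That includes some patients who enter with raised liver values: 5.1.8 admits AST/ALT up to 3 x ULN and bilirubin up to 1.5 x ULN, so a modest rise could qualify.

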#### Hematologic

- a. For patients with baseline/screening absolute neutrophil count (ANC) ≥1000/mm^3, grade 4 neutropenia [ANC <500/mm^3] not responsive to optimal supportive care or G-CSF administration lasting ≥5 days. For patients with baseline/screening ANC <1000/mm^3, DLT here is defined as a ≥75% reduction from baseline ANC not responsive to optimal supportive care or G-CSF administration lasting ≥5 days.
- b. Any grade febrile neutropenia.

- c. For patients with baseline/screening platelet count ≥100,000/mm^3, grade 4 thrombocytopenia (platelet count <25,000/mm^3) lasting ≥7 days. For patients with baseline/screening platelet count <100,000/mm^3, DLT here is defined as a ≥75% reduction from baseline platelet counts lasting for ≥7 days.
- d. Grade  $\geq$ 3 thrombocytopenia-associated bleeding.

Subjects will be considered eligible for DLT assessment if they have received at least 1 dose of RP-3500 and 1 dose of olaparib.

### 4.2.5 Consideration of Alternative Dosing Strategies

Alternative dosing strategies including extended intermittent dosing will be considered should any dose level be deemed unacceptably toxic. A meeting between all investigators, the sponsor, and DSMC will be held to determine and approve alternative DLs. Any alternative DLs evaluated will only do so with an amendment to the protocol and appropriate justification.

If a majority of the review committee deem the combination too toxic at any DL, then the trial may be terminated at that time.

#### 4.2.5.1 Dose Level -1 is Deemed Unacceptable Toxicity

If the number of DLTs incurred at DL-1 is deemed U by the keyboard design decision table, alternative dosing schedules and strategies will be considered. These include adding additional DLs in which RP-3500 is dosed at either 20mg, 30mg, 40mg, or 50mg daily. Depending on the DLTs encountered at DL-1 and if these were attributed to either RP-3500 or olaparib administration, olaparib for these additional DLs can be dosed between 100-200mg BID. The new DLs may have either similar intermittent dosing schedule of the combination with 2 days on and 5 days off or an alternative dosing strategy of the combination of 2 weeks on and 1 week off. Other considerations would include a 28 day cycle in which the dosing would alternate between the 4 weeks (i.e. first week on, second week off, third week on, fourth week off) with dosing being 2-3 days in the "on" weeks.

#### 4.2.5.2 Exploration of Extended Intermittent Dosing

Should DLTs occur at at any DL so that the keyboard algorithm deems that DL unacceptably toxic, an extended intermittent dosing schedule can be considered. While subsequent patients would enroll with the same RP-3500 and olaparib dosages at the current DL, an extended intermittent dosing schedule can be explored in which patients would dose for 2 weeks on and then have a 1 week rest period within a 21-day cycle. In the 2 weeks that patients dose, RP-3500 and olaparib will be administered 2 days during the week with 5 days off (Table 10).

Table 9. Modification of Dosing Schedule for Toxicity	with Every Week Dosing

Dose Level	RP-3500	Olaparib	Dosing Schedule
-1	40mg daily	100mg BID	2 days on/5 days off, every week

	-1A	40mg daily	100mg BID	2 days on/5 days off; 2 weeks on/1 week off
1		50mg daily	100mg BID	2 days on/5 days off, every week
	1A	50mg daily	100mg BID	2 days on/5 days off; 2 weeks on/1 week off
2		80mg daily	100mg BID	2 days on/5 days off, every week
	2A	80mg daily	100mg BID	2 days on/5 days off; 2 weeks on/1 week off
3		80mg daily	150mg BID	2 days on/5 days off, every week
	3A	80mg daily	150mg BID	2 days on/5 days off; 2 weeks on/1 week off

If patients enrolled at the extended intermittent dosing DLs clear a DL, dose escalation may continue but must follow the outlined A DLs in Table 9. Modification of Dosing Schedule for Toxicity with Every Week Dosing(i.e. DL -1A, DL 1A, DL 2A, DL 3A).

# 4.2.5.3 Escalation Beyond DL3

If enrollment of patients reaches DL3 and this DL is deemed safe, consideration for a DL4 in which RP-3500 is dosed at 120mg daily and olaparib is dosed at 150mg BID (2 days per week) will be considered. In this case, 6 additional patients will be added to the phase Ib cohort for a maximum of 24 patients.

## 4.2.5.4 Continuous Dosing

In any of the original and alternative DLs, continuous RP-3500 and/or olaparib dosing (i.e. no days off) may be explored pending the PK, PD and toxicity assessments, and with the approval of the DSMC and amendment to the protocol.

## 4.2.5.5 Intra-patient Dose Escalation

At the discretion of the treating investigator, phase Ib patients enrolled at a lower DL may have their doses of camonsertib (RP-3500) and/or olaparib escalated to the next highest DL that has cleared the DLT window and deemed acceptably safe by the DSMC. Patients may not escalate if they have encountered a decrease in dosages or dose schedule due to treatment-related AEs, or have not been able to maintain their assigned DL dosages and dosing schedule for at least 6 weeks. However, if a patient required a dosing schedule modification (i.e. reduction from every week dosing to 2 weeks on/1 week off) and has not experienced significant treatment-related AEs grade >2 on the new dosing schedule for at least 6 weeks, and the next cleared DL is also a

dosing schedule of 2 weeks on/1 week off, the patient may still escalate their dosages of RP-3500 and/or olaparib to the newly cleared DL.

### 4.3 Phase II Dose Expansion

After completion of the phase Ib portion and assignment of the RP2D, continuous enrollment of patients may commence into the phase II dose expansion portion. All patients enrolled at the RP2D during the phase Ib dose-escalation portion of the trial can be carried over into the phase II analysis. The maximum number of patients that can be carried over from the dose escalation to the dose-expansion portion is 12.

The phase II dose expansion will consist of two separate cohorts of subjects: an enrichment cohort and a cohort for all other eligible subjects. All subjects enrolled into the enrichment cohort must have a del(11q) and/or ATM mutation. Eight subjects will be enrolled into the enrichment cohort and 16 will be enrolled into the second cohort for a total phase II cohort of 24 patients.

### 4.4 Study Duration and Sample Size

With cohorts of 3 patients and possible early completion of the dose-escalation due to a DL accruing 12 patients, then the minimum time to accrue 4 cohorts is 4 months. Due to potential delays in patient enrollment and variability in dose escalation cohort size, the maximum enrollment time frame for the dose escalation portion is anticipated to be 24 months. Expansion at the RP2D is anticipated to be between 6-12 months as a portion of the dose escalation cohort treated at the RP2D will be rolled into the expansion cohort. Therefore, the total study duration is between 12-36 months, which is inclusive of the phase Ib and phase II durations.

On average, we expect 33 patients to be enrolled, assuming that 9 patients in the phase Ib portion will be treated at the MTD and rolled into the dose expansion phase. If the dose escalation portion enrolls patients only at the RP2D and all of these patients are rolled into the dose-expansion cohort, then the minimum number of patients required would be 24 for the entire trial. The maximum number of patients required would be 39 assuming that only 3 patients roll over from the dose escalation to the dose expansion.

#### 4.5 End of Study

A subject is considered to have completed the study if he or she has completed all phases of the study including the last visit or the last scheduled procedure shown in the Schedule of Events

The study will end when the last subject completes the last visit or last contact, discontinues from the study, or is lost to follow-up, whichever occurs first. In addition, the sponsor may terminate the study at any time. If at any time, the sponsor terminates the study any subjects receiving clinical benefit from the study intervention may roll over to an expanded access protocol to ensure continued access to the study medication.

## 4.5.1 Continuation of Study Protocol Treatment Beyond 18 Cycles

If a subject completes 18 cycles of study protocol treatment and is still deriving clinical benefit, the patient may remain on study treatment and follow up at the discretion of the treating provider

indefinitely. Patients may discontinue follow up and treatment as per section 6.9.1 and discontinue the study as per section 6.9.2. All required "EOT" assessments should be performed at the completion of C18D21 including laboratory, imaging and bone marrow assessments. The post-treatment "follow-up" 28 days later is not required.

After cycle 18, the patient should be monitored every 1-3 cycles with physical exam, ECOG PS, vital signs, height/weight and laboratory assessments that are required on previous day 1s (e.g. cycle 4 day 1). Camonsertib (RP-3500) and olaparib may be dispensed to the patient in 1-3 month allotments depending on the intended follow up as determined by the treating investigator. Repeat imaging and bone marrow biopsies are not mandatory during this extended treatment period and should be performed as clinically indicated, following the step-wise approach outlined in footnote 20 of the Schedule of Events.

